		Median	Median	Median	Median	
		Q1, Q3	Q1, Q3	Q1, Q3	Q1, Q3	
		Min, Max	Min, Max	Min, Max	Min, Max	
	Change Week 4	N	N	N	N	
		Mean (SEM)	Mean (SEM)	Mean (SEM)	Mean (SEM)	
		Median	Median	Median	Median	
		Q1, Q3	Q1, Q3	Q1, Q3	Q1, Q3	
		Min, Max	Min, Max	Min, Max	Min, Max	
		Within group p-value+	x.xxx(r)	x.xxx(r)	x.xxx(r)	
		LS Mean (SEM)	LS Mean (SEM)	LS Mean (SEM)	LS Mean (SEM)	x.xxx(r)
		Group comparison p-value*		x.xxx(r)	x.xxx(r)	
		% Change (Week 4)	N	N	N	N
			Mean (SEM)	Mean (SEM)	Mean (SEM)	Mean (SEM)
	Median		Median	Median	Median	
	Q1, Q3		Q1, Q3	Q1, Q3	Q1, Q3	
	Min, Max		Min, Max	Min, Max	Min, Max	
	Within group p-value+		x.xxx(r)	x.xxx(r)	x.xxx(r)	
	LS Mean (SEM)		LS Mean (SEM)	LS Mean (SEM)	LS Mean (SEM)	x.xxx(r)
	Group comparison p-value*		x.xxx(r)	x.xxx(r)		
	Week 8 (Visit 5)	N	N	N	N	
Mean (SEM)		Mean (SEM)	Mean (SEM)	Mean (SEM)		

Table 4.3  
Secondary Outcome Variable: Body Composition (Visits 4, 5, 6, 7) Descriptive Statistics and P-values

Parameter	Week	Control	TSFL	MEDD	Intervention p-value^
		Median	Median	Median	
		Q1, Q3	Q1, Q3	Q1, Q3	
		Min, Max	Min, Max	Min, Max	
	Change Week 8	N	N	N	
		Mean (SEM)	Mean (SEM)	Mean (SEM)	
		Median	Median	Median	
		Q1, Q3	Q1, Q3	Q1, Q3	
		Min, Max	Min, Max	Min, Max	
		Within group p-value+	x.xxx(r)	x.xxx(r)	
		LS Mean (SEM)	LS Mean (SEM)	LS Mean (SEM)	x.xxx(r)
		Group comparison p-value*	x.xxx(r)	x.xxx(r)	
	% Change (Week 8)	N	N	N	
		Mean (SEM)	Mean (SEM)	Mean (SEM)	
		Median	Median	Median	
		Q1, Q3	Q1, Q3	Q1, Q3	
		Min, Max	Min, Max	Min, Max	
		Within group p-value+	x.xxx(r)	x.xxx(r)	
		LS Mean (SEM)	LS Mean (SEM)	LS Mean (SEM)	x.xxx(r)
		Group comparison p-value*	x.xxx(r)	x.xxx(r)	
	Week 12	N	N	N	
	(Visit 6)	Mean (SEM)	Mean (SEM)	Mean (SEM)	
		Median	Median	Median	
		Q1, Q3	Q1, Q3	Q1, Q3	
		Min, Max	Min, Max	Min, Max	
	Change Week 12	N	N	N	
		Mean (SEM)	Mean (SEM)	Mean (SEM)	
		Median	Median	Median	
		Q1, Q3	Q1, Q3	Q1, Q3	
		Min, Max	Min, Max	Min, Max	

Table 4.3  
Secondary Outcome Variable: Body Composition (Visits 4, 5, 6, 7) Descriptive Statistics and P-values

Parameter	Week	Control	TSFL	MEDD	Intervention p-value^
		Within group p-value+	x.xxx(r)	x.xxx(r)	x.xxx(r)
		LS Mean (SEM)	LS Mean (SEM)	LS Mean (SEM)	x.xxx(r)
		Group comparison p-value*		x.xxx(r)	
	% Change (Week 12)	N	N	N	
		Mean (SEM)	Mean (SEM)	Mean (SEM)	
		Median	Median	Median	
		Q1, Q3	Q1, Q3	Q1, Q3	
		Min, Max	Min, Max	Min, Max	
		Within group p-value+	x.xxx(r)	x.xxx(r)	x.xxx(r)
		LS Mean (SEM)	LS Mean (SEM)	LS Mean (SEM)	x.xxx(r)
		Group comparison p-value*		x.xxx(r)	
	Week 16	N	N	N	
	(Visit 7)	Mean (SEM)	Mean (SEM)	Mean (SEM)	
		Median	Median	Median	
		Q1, Q3	Q1, Q3	Q1, Q3	
		Min, Max	Min, Max	Min, Max	
	Change Week 16	N	N	N	
		Mean (SEM)	Mean (SEM)	Mean (SEM)	
		Median	Median	Median	
		Q1, Q3	Q1, Q3	Q1, Q3	
		Min, Max	Min, Max	Min, Max	
		Within group p-value+	x.xxx(r)	x.xxx(r)	x.xxx(r)
		LS Mean (SEM)	LS Mean (SEM)	LS Mean (SEM)	x.xxx(r)
		Group comparison p-value*		x.xxx(r)	
	% Change (Week 16)	N	N	N	
		Mean (SEM)	Mean (SEM)	Mean (SEM)	
		Median	Median	Median	
		Q1, Q3	Q1, Q3	Q1, Q3	
		Min, Max	Min, Max	Min, Max	

Table 4.3  
 Secondary Outcome Variable: Body Composition (Visits 4, 5, 6, 7) Descriptive Statistics and P-values

Parameter	Week	Control	TSFL	MEDD	Intervention p-value ^	
		Within group p-value+	x.xxx(r)	x.xxx(r)	x.xxx(r)	
		LS Mean (SEM)	LS Mean (SEM)	LS Mean (SEM)	LS Mean (SEM)	x.xxx(r)
		Group comparison p-value*		x.xxx(r)	x.xxx(r)	

^ p-values are from ANCOVA models, adjusted for sex and baseline values at Visit 2.

(r) indicates rank transformation was employed.

\* p-values are adjusted for multiple comparisons (each active group vs. control group)

+ p-values are generated from paired t-test or sign-rank test, as appropriate

**NOTE: This table will be presented for body composition measures: total fat mass, total lean mass, percent body fat, android fat and lean mass, gynoid fat and lean mass, and abdominal visceral fat mass and volume.**

Table 4.4  
Secondary Outcome Variables: Body Circumference Parameters (Visits 4, 5, 6, 7) Descriptive Statistics and P-values

Parameter	Week		Control	TSFL	MEDD	Intervention p-value^	
Waist Circumference (cm)	Baseline ( Week 0)	N	N	N	N		
	(Visit 2)	Mean (SEM)	Mean (SEM)	Mean (SEM)	Mean (SEM)	Mean (SEM)	
		Median	Median	Median	Median	Median	
		Q1, Q3	Q1, Q3	Q1, Q3	Q1, Q3	Q1, Q3	
		Min, Max	Min, Max	Min, Max	Min, Max	Min, Max	
	Week 4	N	N	N	N		
	(Visit 4)	Mean (SEM)	Mean (SEM)	Mean (SEM)	Mean (SEM)	Mean (SEM)	
		Median	Median	Median	Median	Median	
		Q1, Q3	Q1, Q3	Q1, Q3	Q1, Q3	Q1, Q3	
		Min, Max	Min, Max	Min, Max	Min, Max	Min, Max	
	Change Week 4	N	N	N	N		
		Mean (SEM)	Mean (SEM)	Mean (SEM)	Mean (SEM)	Mean (SEM)	
		Median	Median	Median	Median	Median	
		Q1, Q3	Q1, Q3	Q1, Q3	Q1, Q3	Q1, Q3	
		Min, Max	Min, Max	Min, Max	Min, Max	Min, Max	
		Within group p-value+	x.xxx(r)	x.xxx(r)	x.xxx(r)	x.xxx(r)	
		LS Mean (SEM)	LS Mean (SEM)	LS Mean (SEM)	LS Mean (SEM)	LS Mean (SEM)	x.xxx(r)
	Group comparison p-value*			x.xxx(r)	x.xxx(r)		
	Week 8	N	N	N	N		
	(Visit 5)	Mean (SEM)	Mean (SEM)	Mean (SEM)	Mean (SEM)	Mean (SEM)	
		Median	Median	Median	Median	Median	
		Q1, Q3	Q1, Q3	Q1, Q3	Q1, Q3	Q1, Q3	
		Min, Max	Min, Max	Min, Max	Min, Max	Min, Max	
	Change Week 8	N	N	N	N		
		Mean (SEM)	Mean (SEM)	Mean (SEM)	Mean (SEM)	Mean (SEM)	
		Median	Median	Median	Median	Median	
		Q1, Q3	Q1, Q3	Q1, Q3	Q1, Q3	Q1, Q3	
		Min, Max	Min, Max	Min, Max	Min, Max	Min, Max	

Table 4.4  
Secondary Outcome Variables: Body Circumference Parameters (Visits 4, 5, 6, 7) Descriptive Statistics and P-values

Parameter	Week	Control	TSFL	MEDD	Intervention p-value ^
		Within group p-value+	x.xxx(r)	x.xxx(r)	x.xxx(r)
		LS Mean (SEM)	LS Mean (SEM)	LS Mean (SEM)	x.xxx(r)
		Group comparison p-value*	x.xxx(r)	x.xxx(r)	
	Week 12	N	N	N	
	(Visit 6)	Mean (SEM)	Mean (SEM)	Mean (SEM)	
		Median	Median	Median	
		Q1, Q3	Q1, Q3	Q1, Q3	
		Min, Max	Min, Max	Min, Max	
	Change Week 12	N	N	N	
		Mean (SEM)	Mean (SEM)	Mean (SEM)	
		Median	Median	Median	
		Q1, Q3	Q1, Q3	Q1, Q3	
		Min, Max	Min, Max	Min, Max	
		Within group p-value+	x.xxx(r)	x.xxx(r)	x.xxx(r)
		LS Mean (SEM)	LS Mean (SEM)	LS Mean (SEM)	x.xxx(r)
		Group comparison p-value*	x.xxx(r)	x.xxx(r)	
	Week 16	N	N	N	
	(Visit 7)	Mean (SEM)	Mean (SEM)	Mean (SEM)	
		Median	Median	Median	
		Q1, Q3	Q1, Q3	Q1, Q3	
		Min, Max	Min, Max	Min, Max	
	Change Week 16	N	N	N	
		Mean (SEM)	Mean (SEM)	Mean (SEM)	
		Median	Median	Median	
		Q1, Q3	Q1, Q3	Q1, Q3	
		Min, Max	Min, Max	Min, Max	
		Within group p-value+	x.xxx(r)	x.xxx(r)	x.xxx(r)
		LS Mean (SEM)	LS Mean (SEM)	LS Mean (SEM)	x.xxx(r)
		Group comparison p-value*	x.xxx(r)	x.xxx(r)	

^ p-values are from ANCOVA models, adjusted for sex and baseline values at Visit 2.

Table 4.4

Secondary Outcome Variables: Body Circumference Parameters (Visits 4, 5, 6, 7) Descriptive Statistics and P-values

(r) indicates rank transformation was employed.

\* p-values are NOT adjusted for multiple comparisons

+ p-values are generated from paired t-test or sign-rank test, as appropriate

**NOTE: This table will be presented for body circumference parameters: waist circumference, hip circumference, chest circumference, dominant upper arm circumference, dominant thigh circumference, total body circumference (sum of all five measures), and waist to hip ratio.**

Table 4.5  
Secondary Outcome Variable: hs-CRP (Visit 7) Descriptive Statistics and P-values

Parameter	Week		Control	TSFL	MEDD	Intervention p-value ^
hs-CRP (mg/L)	Baseline ( Week 0) (Visit 2)	N	N	N	N	
		Mean (SEM)	Mean (SEM)	Mean (SEM)	Mean (SEM)	
		Median	Median	Median	Median	
		Q1, Q3	Q1, Q3	Q1, Q3	Q1, Q3	
		Min, Max	Min, Max	Min, Max	Min, Max	
	Week 16 (Visit 7)	N	N	N	N	
		Mean (SEM)	Mean (SEM)	Mean (SEM)	Mean (SEM)	
		Median	Median	Median	Median	
		Q1, Q3	Q1, Q3	Q1, Q3	Q1, Q3	
		Min, Max	Min, Max	Min, Max	Min, Max	
	Change (Week 16)	N	N	N	N	
		Mean (SEM)	Mean (SEM)	Mean (SEM)	Mean (SEM)	
		Median	Median	Median	Median	
		Q1, Q3	Q1, Q3	Q1, Q3	Q1, Q3	
		Min, Max	Min, Max	Min, Max	Min, Max	
		Within group p-value +	x.xxx(r)	x.xxx(r)	x.xxx(r)	
		LS Mean (SEM)	LS Mean (SEM)	LS Mean (SEM)	LS Mean (SEM)	x.xxx(r)
	Group comparison p-value *			x.xxx(r)	x.xxx(r)	

^ p-values are from ANCOVA models, adjusted for sex and baseline values at Visit 2

(r) indicates rank transformation was employed.

\* p-values are NOT adjusted for multiple comparisons

+ p-values are generated from paired t-test or sign-rank test, as appropriate

Table 4.6  
Secondary Outcome Variable: IWQoL-Lite Questionnaire Outcomes (Visits 5 and 7) Descriptive Statistics and P-values

Parameter	Week	Control	TSFL	MEDD	Intervention p-value^
IWQoL Total Score	Baseline ( Week 0) (Visit 2)	N	N	N	N
		Mean (SEM)	Mean (SEM)	Mean (SEM)	Mean (SEM)
		Median	Median	Median	Median
		Q1, Q3	Q1, Q3	Q1, Q3	Q1, Q3
		Min, Max	Min, Max	Min, Max	Min, Max
	Week 8 (Visit 5)	N	N	N	N
		Mean (SEM)	Mean (SEM)	Mean (SEM)	Mean (SEM)
		Median	Median	Median	Median
		Q1, Q3	Q1, Q3	Q1, Q3	Q1, Q3
		Min, Max	Min, Max	Min, Max	Min, Max
	Change Week 8	N	N	N	N
		Mean (SEM)	Mean (SEM)	Mean (SEM)	Mean (SEM)
		Median	Median	Median	Median
		Q1, Q3	Q1, Q3	Q1, Q3	Q1, Q3
		Min, Max	Min, Max	Min, Max	Min, Max
		Within group p-value+	x.xxx(r)	x.xxx(r)	x.xxx(r)
		LS Mean (SEM)	LS Mean (SEM)	LS Mean (SEM)	LS Mean (SEM)
	Group comparison p-value*		x.xxx(r)	x.xxx(r)	
	Week 16 (Visit 7)	N	N	N	N
		Mean (SEM)	Mean (SEM)	Mean (SEM)	Mean (SEM)
		Median	Median	Median	Median
		Q1, Q3	Q1, Q3	Q1, Q3	Q1, Q3
		Min, Max	Min, Max	Min, Max	Min, Max
	Change Week 16	N	N	N	N
		Mean (SEM)	Mean (SEM)	Mean (SEM)	Mean (SEM)
		Median	Median	Median	Median
		Q1, Q3	Q1, Q3	Q1, Q3	Q1, Q3
		Min, Max	Min, Max	Min, Max	Min, Max
Within group p-value+	x.xxx(r)	x.xxx(r)	x.xxx(r)		

Table 4.6  
 Secondary Outcome Variable: IWQoL-Lite Questionnaire Outcomes (Visits 5 and 7) Descriptive Statistics and P-values

Parameter	Week	Control	TSFL	MEDD	Intervention p-value ^
		LS Mean (SEM)	LS Mean (SEM)	LS Mean (SEM)	x.xxx(r)
		Group comparison p-value*	x.xxx(r)	x.xxx(r)	

^ p-values are from ANCOVA models, adjusted for sex and baseline values at Visit 2.

(r) indicates rank transformation was employed.

\* p-values are NOT adjusted for multiple comparisons (each active group vs. control group)

+ p-values are generated from paired t-test or sign-rank test, as appropriate

**NOTE: This table will be presented for IWQOL-Lite total score and five scale scores (Physical Function, Self-Esteem, Sexual Life, Public Distress, and Work).**

Table 4.7  
Secondary Outcome Variable: RAND Questionnaire Outcomes (Visits 5 and 7) Descriptive Statistics and P-values

Parameter	Week		Control	TSFL	MEDD	Intervention p-value^
Physical Functioning	Baseline ( Week 0) (Visit 2)	N	N	N	N	
		Mean (SEM)	Mean (SEM)	Mean (SEM)	Mean (SEM)	
		Median	Median	Median	Median	
		Q1, Q3	Q1, Q3	Q1, Q3	Q1, Q3	
		Min, Max	Min, Max	Min, Max	Min, Max	
	Week 8 (Visit 5)	N	N	N	N	
		Mean (SEM)	Mean (SEM)	Mean (SEM)	Mean (SEM)	
		Median	Median	Median	Median	
		Q1, Q3	Q1, Q3	Q1, Q3	Q1, Q3	
		Min, Max	Min, Max	Min, Max	Min, Max	
	Change Week 8	N	N	N	N	
		Mean (SEM)	Mean (SEM)	Mean (SEM)	Mean (SEM)	
		Median	Median	Median	Median	
		Q1, Q3	Q1, Q3	Q1, Q3	Q1, Q3	
		Min, Max	Min, Max	Min, Max	Min, Max	
		Within group p-value+	x.xxx(r)	x.xxx(r)	x.xxx(r)	
		LS Mean (SEM)	LS Mean (SEM)	LS Mean (SEM)	LS Mean (SEM)	x.xxx(r)
	Group comparison p-value*		x.xxx(r)	x.xxx(r)		
	Week 16 (Visit 7)	N	N	N	N	
		Mean (SEM)	Mean (SEM)	Mean (SEM)	Mean (SEM)	
		Median	Median	Median	Median	
		Q1, Q3	Q1, Q3	Q1, Q3	Q1, Q3	
		Min, Max	Min, Max	Min, Max	Min, Max	
	Change Week 16	N	N	N	N	
		Mean (SEM)	Mean (SEM)	Mean (SEM)	Mean (SEM)	
		Median	Median	Median	Median	
		Q1, Q3	Q1, Q3	Q1, Q3	Q1, Q3	
		Min, Max	Min, Max	Min, Max	Min, Max	
	Within group p-value+	x.xxx(r)	x.xxx(r)	x.xxx(r)		

Table 4.7  
 Secondary Outcome Variable: RAND Questionnaire Outcomes (Visits 5 and 7) Descriptive Statistics and P-values

Parameter	Week	Control	TSFL	MEDD	Intervention p-value ^
		LS Mean (SEM)	LS Mean (SEM)	LS Mean (SEM)	x.xxx(r)
		Group comparison p-value*		x.xxx(r)	x.xxx(r)

^ p-values are from ANCOVA models, adjusted for sex and baseline values at Visit 2.

(r) indicates rank transformation was employed.

\* p-values are NOT adjusted for multiple comparisons (each active group vs. control group)

+ p-values are generated from paired t-test or sign-rank test, as appropriate

**NOTE: This table will be presented for the eight scale scores of the RAND questionnaire (Physical functioning, Role limitations due to physical health, Role limitations due to emotional Problems, Energy/fatigue, Emotional well-being, Social functioning, Pain, General health).**

Table 4.8.1  
 Secondary Outcome Variable: Satisfaction and Health/Well-being Questionnaire Descriptive Statistics

Parameter	Week	Rating	Control	TSFL	MEDD
Recommend Weight Loss Plan	Week 16 (Visit 7)	Strongly Disagree	N (%)	N (%)	N (%)
		Disagree	N (%)	N (%)	N (%)
		Neither Agree or Disagree	N (%)	N (%)	N (%)
		Agree	N (%)	N (%)	N (%)
		Strongly Agree	N (%)	N (%)	N (%)

NOTE: This table will be presented for ratings for each question of the Satisfaction and Health/Well-being questionnaire.

Table 4.8.2  
 Secondary Outcome Variable: Satisfaction and Health/Well-being Questionnaire (Recoded) Descriptive Statistics and P-values

Parameter	Week	Rating	Control	TSFL	MEDD	Intervention p-value
Recommend Weight Loss Plan	Week 16 (Visit 7)	Disagree	N (%)	N (%)	N (%)	x.xxx
		Neither Agree or Disagree	N (%)	N (%)	N (%)	
		Agree	N (%)	N (%)	N (%)	
		Group comparison p-value*		x.xxx	x.xxx	

\* p-values are NOT adjusted for multiple comparisons

NOTE: This table will be presented for ratings for each question of the Satisfaction and Health/Well-being questionnaire.

Table 4.9  
Secondary Outcome Variable: Program Questionnaire (Visits 4, 5, 6, 7) Descriptive Statistics

Parameter	Week		Control	TSFL	MEDD
Physical Activity Level	Baseline ( Week 0)	N	N	N	N
	(Visit 2)	Mean (SEM)	Mean (SEM)	Mean (SEM)	Mean (SEM)
		Median	Median	Median	Median
		Q1, Q3	Q1, Q3	Q1, Q3	Q1, Q3
		Min, Max	Min, Max	Min, Max	Min, Max
	Week 4	N	N	N	N
	(Visit 4)	Mean (SEM)	Mean (SEM)	Mean (SEM)	Mean (SEM)
		Median	Median	Median	Median
		Q1, Q3	Q1, Q3	Q1, Q3	Q1, Q3
		Min, Max	Min, Max	Min, Max	Min, Max
	Week 8	N	N	N	N
	(Visit 5)	Mean (SEM)	Mean (SEM)	Mean (SEM)	Mean (SEM)
		Median	Median	Median	Median
		Q1, Q3	Q1, Q3	Q1, Q3	Q1, Q3
		Min, Max	Min, Max	Min, Max	Min, Max
	Week 12	N	N	N	N
	(Visit 6)	Mean (SEM)	Mean (SEM)	Mean (SEM)	Mean (SEM)
		Median	Median	Median	Median
		Q1, Q3	Q1, Q3	Q1, Q3	Q1, Q3
		Min, Max	Min, Max	Min, Max	Min, Max
Week 16	N	N	N	N	
(Visit 7)	Mean (SEM)	Mean (SEM)	Mean (SEM)	Mean (SEM)	
	Median	Median	Median	Median	
	Q1, Q3	Q1, Q3	Q1, Q3	Q1, Q3	
	Min, Max	Min, Max	Min, Max	Min, Max	
VAS	Week 4	N	N	N	N
	(Visit 4)	Mean (SEM)	Mean (SEM)	Mean (SEM)	Mean (SEM)
		Median	Median	Median	Median
		Q1, Q3	Q1, Q3	Q1, Q3	Q1, Q3

Table 4.9  
Secondary Outcome Variable: Program Questionnaire (Visits 4, 5, 6, 7) Descriptive Statistics

Parameter	Week	Control	TSFL	MEDD	
		Min, Max	Min, Max	Min, Max	
	Week 8	N	N	N	
	(Visit 5)	Mean (SEM)	Mean (SEM)	Mean (SEM)	Mean (SEM)
		Median	Median	Median	Median
		Q1, Q3	Q1, Q3	Q1, Q3	Q1, Q3
		Min, Max	Min, Max	Min, Max	Min, Max
	Week 12	N	N	N	
	(Visit 6)	Mean (SEM)	Mean (SEM)	Mean (SEM)	Mean (SEM)
		Median	Median	Median	Median
		Q1, Q3	Q1, Q3	Q1, Q3	Q1, Q3
		Min, Max	Min, Max	Min, Max	Min, Max
	Week 16	N	N	N	
	(Visit 7)	Mean (SEM)	Mean (SEM)	Mean (SEM)	Mean (SEM)
		Median	Median	Median	Median
		Q1, Q3	Q1, Q3	Q1, Q3	Q1, Q3
		Min, Max	Min, Max	Min, Max	Min, Max
Meal Replacement	Week 4	N	N	N	
	(Visit 4)	Mean (SEM)	Mean (SEM)	Mean (SEM)	Mean (SEM)
		Median	Median	Median	Median
		Q1, Q3	Q1, Q3	Q1, Q3	Q1, Q3
		Min, Max	Min, Max	Min, Max	Min, Max
	Week 8	N	N	N	
	(Visit 5)	Mean (SEM)	Mean (SEM)	Mean (SEM)	Mean (SEM)
		Median	Median	Median	Median
		Q1, Q3	Q1, Q3	Q1, Q3	Q1, Q3
		Min, Max	Min, Max	Min, Max	Min, Max
	Week 12	N	N	N	
	(Visit 6)	Mean (SEM)	Mean (SEM)	Mean (SEM)	Mean (SEM)
		Median	Median	Median	Median

Table 4.9  
 Secondary Outcome Variable: Program Questionnaire (Visits 4, 5, 6, 7) Descriptive Statistics

Parameter	Week	Control	TSFL	MEDD
		Q1, Q3	Q1, Q3	Q1, Q3
		Min, Max	Min, Max	Min, Max
	Week 16	N	N	N
	(Visit 7)	Mean (SEM)	Mean (SEM)	Mean (SEM)
		Median	Median	Median
		Q1, Q3	Q1, Q3	Q1, Q3
		Min, Max	Min, Max	Min, Max

Table 4.10  
Secondary Outcome Variable: Weight Loss Program Adherence Descriptive Statistics and P-values

Parameter		TSFL	MEDD
Meal Replacement^	Mean (SEM)	Mean (SEM)	Mean (SEM)
	Median	Median	Median
	Q1, Q3	Q1, Q3	Q1, Q3
	Min, Max	Min, Max	Min, Max
	Corr (p-value)+	0.xxx (x.xxx)	0.xxx (x.xxx)
Nutrition Support Contact	Mean (SEM)	Mean (SEM)	Mean (SEM)
	Median	Median	Median
	Q1, Q3	Q1, Q3	Q1, Q3
	Min, Max	Min, Max	Min, Max
Coaching Contact	Mean (SEM)	Mean (SEM)	
	Median	Median	
	Q1, Q3	Q1, Q3	
	Min, Max	Min, Max	
	Corr (p-value)+	0.xxx (x.xxx)	

^average meal replacement (per day) across the 16-weeks of the study

+spearman's rank-order correlation between the corresponding parameter and absolute change in body weight from baseline (Visit 2; week 0) to end of study (Visit 7; week 16)

Table 4.11  
Secondary Outcome Variable: Nutrition Support Contact P-values

Group	Parameter	Initial & Discretionary NS contact*		Initial NS contact or None**	p-value^
MEDD	% weight loss >= 5%	N (%)	N (%)	N (%)	x.xxx
TSFL	% weight loss >= 5%	N (%)	N (%)	N (%)	x.xxx

^p-values shown are generated from Fisher's exact test

\*at least two NS contacts for MEDD or at least one NS contact for TSFL

\*\*at most one NS contact for MEDD or none for TSFL

Table 5  
Summary of Subjects with at Least One Intervention-emergent Adverse Events

	Control	TSFL	MEDD	Intervention p-value*
Any Adverse Event	N (%)	N (%)	N (%)	x.xxx
Serious	N (%)	N (%)	N (%)	x.xxx
Severe	N (%)	N (%)	N (%)	x.xxx
Related to Study Treatment*	N (%)	N (%)	N (%)	x.xxx

\*p-values shown are generated from Chi-Square or Fisher's exact test, as appropriate

\* Probably or Definitely Related to Study Treatment.

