Participants randomized to the MEDD group will be assigned to the Medifast AchieveTM Plan (4 & 2 & 1 Plan"') for weight loss. Study-specific printed materials (including the "Getting Started Instructions"), will be dispensed at Visit 2 (week 0) along with a starter meal kit containing approximately one week's worth of study foods (see Supplementary Materials). Participants will place an order for the following four weeks' worth of study foods with additional study foods ordered throughout the study. Following the clinic visit, participants randomized to this group will be instructed to contact the Medifast Nutrition Support Team by telephone prior to 17:00 h EST to receive an overview of the weight loss program. This telephone call (10-15 min in length) will take place the day of Visit 2 (week 0) as participants will be instructed to start their weight loss program on the day following the randomization visit (day 1). Participants will also have telephone and e-mail access to the Medifast Nutrition Support Team (at the participants' discretion) and Medifast online tools throughout the study. Participants in the MEDD group will be encouraged to track weight and food intake and access MEDD written, online, and virtual support tools to use at their discretion. More details on the MEDD program can be found in Section 6.4.1.

Clinic Visits (Visit 3, 4, 5, 6 and 7; weeks 2, 4, 8, 12, and 16)

At Visit 3 (week 2), participants will arrive at the clinic fasted $(12 \pm 2 h, water only, anchored to time of gown body weight measurement) to undergo clinic visit procedures (evaluations of inclusion/exclusion criteria, concomitant medication/supplement use, vital signs, and AEs). Gown body weight will be measured.$

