Participants will be dispensed study-specific printed materials (including the “Getting Started Instructions”) at Visit 2 (week 0) and will have one telephone call with a Medifast Nutrition Support Team member prior to 17:00 h EST at Visit 2 (week 0) to receive instruction on the meal plan and support materials as participants will be instructed to start their weight loss program on the day following the randomization visit (day 1). If the telephone call does not take place, participants will be instructed to start their weight loss program on day 1 regardless (a protocol deviation form must be submitted). Participants will also have telephone and e-mail access to the Medifast Nutrition Support Team and Medifast online tools throughout the study. Participants in the MEDD group will be encouraged to track weight and food intake and access MEDD written, online, and virtual support tools to use at their discretion.

- **Control:** The Control group will follow a self-directed diet, which is a food-based, reduced-calorie diet, consistent with the 2015 Dietary Guidelines for Americans (See Supplementary Materials). This group will receive a one-on-one personal instruction session (10-15 min) with a trained member of the study staff at the Visit 2 (week 0) clinic visit. During this session, daily energy intake targets will be determined for each participant using the National Institutes of Health body weight planner ([www.niddk.nih.gov/health-information/health-topics/weight-control/body-weight-planner/Pages/bwp.aspx](http://www.niddk.nih.gov/health-information/health-topics/weight-control/body-weight-planner/Pages/bwp.aspx)). The personalized daily energy intake level will be specific to each participant’s 16-week weight loss goal, targeting 7% weight loss over the 16-week weight loss period, consistent with recent obesity treatment guidelines (Jensen 2014). Participants will receive publicly available information from the USDA Choose MyPlate

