Descriptive statistics will be provided for the Program Questionnaire outcomes. Also, linear association between change (absolute) in body weight from baseline (Visit 2; week 0) to end of study (Visit 7; week 16) and average meal replacements [averaged across Visits 4 to 7 (weeks 4-16)] will be obtained (spearman's rank-order correlation) for the MEDD and TSFL groups. Additionally, for the TSFL group, linear association between change (absolute) in body weight from baseline (Visit 2; week 0) to end of study (Visit 7; week 16) and number of coaching contacts will be obtained (spearman's rank-order correlation). Lastly, for the MEDD group, association between whether subjects made discretionary Nutrition Support contact(s) or not and weight loss of  $\geq 5\%$  will be assessed using a Fisher's exact test.

Assumption of normality of residuals will be investigated for each outcome variable at the 5% level of significance with the Shapiro-Wilk test (Shapiro 1965). If the normality assumption is not satisfied, then an analysis based on ranks will be performed.

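### Table 4.11 identifies discretionary Nutrition Support use in MEDD by total contacts, which misplaces a participant who missed the introduction call and later made exactly one discretionary contact

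*SAP*

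**What the plan says.** SAP Section 9.0 describes the MEDD analysis as the "association between whether subjects made discretionary Nutrition Support contact(s) or not", set against weight loss of at least 5% and tested with Fisher's exact test. The variable is a yes/no on discretionary contact.

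The Table 4.11 shell in SAP Section 17.0 puts this into practice through two footnotes. The discretionary column is "at least two NS contacts for MEDD or at least one NS contact for TSFL". The comparison column, headed "Initial NS contact or None", is "at most one NS contact for MEDD or none for TSFL". Both are counts of all contacts, whatever their purpose.

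In MEDD one contact is assigned: an introduction call of 10 to 15 minutes on the day of Visit 2 (Protocol Sections 6.1 and 6.4.1). SAP Section 2.0 provides for its absence: "If the telephone call does not take place, participants will be instructed to start their weight loss program on day 1 regardless", with a protocol deviation form. Protocol Section 6.4.1 says the same. Later access does not depend on that call: "Participants will also have telephone and e-mail access to the Medifast Nutrition Support Team and Medifast online tools throughout the study". Protocol Sections 6.1 and 6.4.1 describe this later use as being at the participant's discretion.

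TSFL has no assigned Nutrition Support call. Table 4.11 nevertheless has a TSFL row with a p-value, although Section 9.0 plans the test for MEDD only.

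**The concern.** The threshold of two contacts works by subtraction: one contact is presumed to be the introduction, so anything beyond it must be discretionary. The presumption fails for a participant who had no introduction. If that person later chose to contact the team once, the total is one and the table records no discretionary use. The participant does not fit the column's own label either, having had neither an initial contact nor no contact.

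Nutrition Support utilisation is a listed secondary outcome (SAP Section 8.2), and Table 4.11 prints a p-value for its association with response. The two groups in that test should be the ones Section 9.0 names. The primary weight comparison is not involved.

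**Working it through.** The documents state no figure that depends on this rule, so there is none to reproduce. The check is to compare the two definitions case by case.

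**Step 1: compare the rules.** Let I = 1 if the introduction took place and 0 if not, and let D = the number of discretionary contacts. Table 4.11 classes a MEDD participant as discretionary if I + D ≥ 2. Section 9.0 does so if D ≥ 1.

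| I | D | I + D | Table 4.11 | Section 9.0 | Agree? |
|---|---|---|---|---|---|
| 0 | 0 | 0 | not discretionary | no | yes |
| 0 | 1 | 1 | not discretionary | yes | **no** |
| 0 | 2 | 2 | discretionary | yes | yes |
| 1 | 0 | 1 | not discretionary | no | yes |
| 1 | 1 | 2 | discretionary | yes | yes |
| 1 | 2 | 3 | discretionary | yes | yes |

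One of the six combinations disagrees: no introduction and exactly one discretionary contact. For TSFL, which has no assigned call, a threshold of one contact is correct.

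**Step 2: how many participants?** This cannot be computed, because no missed-call rate is given. As an assumption only, suppose 5% to 20% of the 66 randomised to MEDD miss the call (66 × 0.05 = 3.3; 66 × 0.20 = 13.2) and one third to one half of those later make exactly one discretionary contact. The range is 3.3 × 1/3 = 1.1 to 13.2 × 1/2 = 6.6, or about 1 to 7 people. SAP Section 16.0 plans the table for the modified ITT and completer sets, so the denominator may be below 66.

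**Step 3: what could it do to the test?** Assume 55 MEDD participants, with 20 of 25 discretionary users and 14 of 30 others reaching 5% loss. Fisher's exact test, two-sided, gives p = 0.0139. Now move three true discretionary users into the comparison column:

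| Responders moved | Non-responders moved | Discretionary column | Comparison column | p |
|---|---|---|---|---|
| 3 | 0 | 17/22 | 17/33 | 0.088 |
| 2 | 1 | 18/22 | 16/33 | 0.022 |
| 1 | 2 | 19/22 | 15/33 | 0.004 |
| 0 | 3 | 20/22 | 14/33 | 0.0005 |

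A second assumed table has 66 participants, with 19 of 24 users and 21 of 42 others responding. Participants are moved at roughly the users' own response rate, rounded to whole people. The p-value is 0.035 with none moved, 0.038 with one, 0.064 with two, 0.054 with four and 0.097 with six.

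If the misplaced participants respond like other discretionary users, the contrast tends to be diluted. If they respond less often, it can be exaggerated. The documents do not say which to expect.

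**The case against.** **A late first call may be the introduction itself.** Protocol Section 6.4.1 describes the assigned call as a one-to-one introduction to the programme. Someone who missed it on the day and calls later may be receiving that introduction, and a count of one then belongs in the comparison column. This stands in part. It limits the error to participants whose single contact was not a delayed introduction, and it means that a rule based only on date would create a new error. It does not rescue the footnotes, since neither document says that a later first contact is to be treated as the introduction.

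**Missed calls should be uncommon and traceable.** Each requires a deviation form. This stands, and it makes the repair easier. A reader might infer that the test no longer answers the question in Section 9.0. That goes too far: five of the six combinations are classified correctly.

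**The effect on significance can be overstated.** A reader might take the move from 0.014 to 0.088 as the expected result. It arises only when all three misplaced participants are responders. With two responders and one non-responder, p is 0.022.

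**Two further criticisms are tempting but unsupported.** One is that an introduction spread over two calls would count as discretionary; the documents describe a single call and no split introduction. The other is that Table 4.10 should not include the assigned MEDD call in its contact summary. The listed outcome is utilisation of Nutrition Support, total contacts is a legitimate summary of that, and the row carries no test.

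**Conclusion.** The point holds in a narrow form. The Table 4.11 footnotes do not implement the MEDD variable in SAP Section 9.0 when the introduction call did not take place. They misplace participants with no introduction and exactly one discretionary contact. This is an error in a stated rule, not just an omitted detail, because the footnotes assign that participant to a column.

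Its importance is small. The analysis is one secondary, non-randomised association within one arm. The number affected is unknown; the 1 to 7 above rests wholly on assumed rates. The direction of the effect on the p-value is open, so the error cannot be dismissed as conservative or presented as hiding an association. The TSFL p-value in Table 4.11 is a separate inconsistency with Section 9.0.

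**What to change.** 1. Redefine the two MEDD columns in the Table 4.11 footnotes as at least one Nutrition Support contact other than the introduction call, versus no such contact. Keep the TSFL definition.
2. Classify by the purpose of the contact. A delayed introduction counts as the introduction, not as discretionary use. Use the deviation forms to identify participants who missed the Visit 2 call.
3. If the contact record does not hold purpose, classify by contact date and add a sensitivity analysis without the participants who missed the Visit 2 call.
4. Reconcile the TSFL row with Section 9.0: either add the TSFL test to the text or remove its p-value from the shell.

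The cost is two footnotes, one sentence in Section 9.0 if the TSFL test is kept, and a small derivation. The main risk is that the derivation depends on what the contact record holds, which the documents do not describe. The date-based fallback is weaker because it would count a delayed introduction as discretionary, hence the sensitivity analysis.
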